1. PURPOSE

The purpose of this SAP addendum is to describe additional analyses not planned as part of the original SAP as well as changes to analyses planned in the SAP.

Table 14.1-1 will be modified to include the per-protocol analysis set. Table A indicates the template tables (from SAP) to be produced and the table number and title for the per-protocol analysis set.

Table A: Templates and Titles for Per-protocol Efficacy Analysis Set Tables

| SAP Template Number | Per-protocol Analysis Set Table Number and Title |
|---------------------|--|
| 14.2-1.1.1 | 14.2-1.1.6: Analysis of AUC of NRS Pain Intensity Scores through 48 hours – Per-protocol Efficacy Analysis Set |
| 14.2-1.2 | 14.2-1.2.1: Summary of AUC of NRS Pain Intensity Scores through 48 hours – Per-protocol Efficacy Analysis Set - Analysis of Variance (ANOVA) Model Results |
| | 14.2-2.2.1: Summary of AUC of NRS Pain Intensity Scores through 24 hours – Per-protocol Efficacy Analysis Set - Analysis of Variance (ANOVA) Model Results |
| | 14.2-3.2.1: Summary of AUC of NRS Pain Intensity Scores through 72 hours – Per-protocol Efficacy Analysis Set - Analysis of Variance (ANOVA) Model Results |
| 14.2-1.3 | 14.2-1.3.1: Summary of AUC of NRS Pain Intensity Scores through 48 hours by Site – Per-protocol Efficacy Analysis Set |
| | 14.2-2.3.1: Summary of AUC of NRS Pain Intensity Scores through 24 hours by Site – Per-protocol Efficacy Analysis Set |
| | 14.2-3.3.1: Summary of AUC of NRS Pain Intensity Scores through 72 hours by Site – Per-protocol Efficacy Analysis Set |
| 14.2-5.1 | 14.2-5.1.1: Analysis of Opioid-Free Subjects through 24 hours – Per-protocol Efficacy Analysis Set |
| | 14.2-5.2.1: Analysis of Opioid-Free Subjects through 48 hours – Per-protocol Efficacy Analysis Set |
| | 14.2-5.3.1: Analysis of Opioid-Free Subjects through 72 hours – Per-protocol Efficacy Analysis Set |
| 14.2-6.1 | 14.2-6.1.1: Summary of Numerical Rating Scale (NRS) Pain Intensity Scores - By Assessment Timepoint – Per-protocol Efficacy Analysis Set |
| 14.2-6.2 | 14.2-6.2.1: Summary of Numerical Rating Scale (NRS) Pain Intensity Scores at Rescue – Per-protocol Efficacy Analysis Set |
| 14.2-7.1 | 14.2-7.1.1: Summary of AUC(0.25-96) and AUC(0.25-Day 10) of NRS Pain Intensity Scores – Per-protocol Efficacy Analysis Set |
| 14.2-7.2 | 14.2-7.2.1: Summary of AUC(24-48) and AUC(48-72) of NRS Pain Intensity Scores Scores – Per-protocol Efficacy Analysis Set |

| | |
|---------------------|--|
| SAP Template Number | Per-protocol Analysis Set Table Number and Title |
| 14.2-8 | 14.2-8.1: Tabulation of Pain-Free Subjects at Assessment Time Points Scores – Per-protocol Efficacy Analysis Set |
| 14.2-9 | 14.2-9.1: Summary of Time to First Rescue Medication Use (hours) Scores – Per-protocol Efficacy Analysis Set |
| 14.2-10 | 14.2-10.1: Summary of Integrated Rank Assessment of NRS Pain Intensity Scores and Opioid Use Scores – Per-protocol Efficacy Analysis Set |
| 14.2-11 | 14.2-11.1: Summary of Satisfaction with Postsurgical Pain Control Questionnaire Score by Timepoint – Per-protocol Efficacy Analysis Set |
| 14.2-12.1 | 14.2-12.1.1: Summary of Postoperative Symptom Severity (PoSSe) Questionnaire - Total Score [1] Summary – Per-protocol Efficacy Analysis Set |
| 14.2-12.2 | 14.2-12.2.1: Summary of Postoperative Symptom Severity (PoSSe) Questionnaire - Individual Question Score Tabulation – Per-protocol Efficacy Analysis Set |
| 14.2-13 | 14.2-13.1: Summary of Number of Unscheduled Phone Calls or Office Visits Related to Pain – Per-protocol Efficacy Analysis Set |
| 14.2-14.1 | 14.2-14.1.1: Summary of Total Rescue Medication Consumption (MED) – Per-protocol Efficacy Analysis Set |
| 14.2-14.2 | 14.2-14.2.1: Summary of the Number of Times Rescue Medication was Used by Subject – Per-protocol Efficacy Analysis Set |

3. ADDITIONAL SUMMARIES

The effect of surgeon will be determined by replacing the site effect in the efficacy analysis of variance with surgeon and by summarizing data by surgeon within site as appropriate (see Section 2 for additional detail). Table B indicated the tables and figures to be produced to explore the surgeon effect and, if applicable, the corresponding table or figure template with a brief description of changes to the planned output.

Table B: Templates and Titles for Surgeon Tables

| | |
|--|------------|
| Surgeon Effect Notes | Table |
| | 14.1-2.1 |
| | 14.1-2.2.1 |
| | 14.1-2.2.2 |
| | 14.1-2.3 |
| These tables will be amended with additional information. The current data planned remains on the table. | 14.1-2.4 |

| | |
|---|---|
| For site 100 create new pages in the table for each surgeon at site 100. The site 100 page will remain as is unchanged. | 14.1-3.1 |
| | 14.1-3.2.1 |
| | 14.1-3.2.2 |
| | 14.1-3.3 |
| Replace site effect in ANOVA with surgeon | 14.2-1.1.1.S: Analysis of AUC of NRS Pain Intensity Scores through 48 hours – Primary Efficacy Analysis Set – Surgeon Effect |
| | 14.2-1.1.6.S: Analysis of AUC of NRS Pain Intensity Scores through 48 hours – Per-protocol Efficacy Analysis Set – Surgeon Effect |
| | 14.2-1.2.1.S: Summary of AUC of NRS Pain Intensity Scores through 48 hours – Primary Efficacy Analysis Set - Analysis of Variance (ANOVA) Model Results – Surgeon Effect |
| | 14.2-1.2.1.S.1: Summary of AUC of NRS Pain Intensity Scores through 48 hours – Per-protocol Efficacy Analysis Set - Analysis of Variance (ANOVA) Model Results – Surgeon Effect |
| | 14.2-2.2.S: Summary of AUC of NRS Pain Intensity Scores through 24 hours – Primary Efficacy Analysis Set - Analysis of Variance (ANOVA) Model Results – Surgeon Effect |
| | 14.2-2.2.1.S: Summary of AUC of NRS Pain Intensity Scores through 24 hours – Per-protocol Efficacy Analysis Set - Analysis of Variance (ANOVA) Model Results – Surgeon Effect |
| | 14.2-3.2.S: Summary of AUC of NRS Pain Intensity Scores through 72 hours – Primary Efficacy Analysis Set - Analysis of Variance (ANOVA) Model Results – Surgeon Effect |
| | 14.2-3.2.1.2: Summary of AUC of NRS Pain Intensity Scores through 72 hours – Per-protocol Efficacy Analysis Set - Analysis of Variance (ANOVA) Model Results – Surgeon Effect |
| Replace site as stratification with surgeon | 14.2-5.1.S: Analysis of Opioid-Free Subjects through 24 hours – Primary Efficacy Analysis Set – Surgeon Effect |
| | 14.2-5.1.1.S: Analysis of Opioid-Free Subjects through 24 hours – Per-protocol Efficacy Analysis Set – Surgeon Effect |
| | 14.2-5.2.S: Analysis of Opioid-Free Subjects through 48 hours – Primary Efficacy Analysis Set |
| | 14.2-5.2.1.S: Analysis of Opioid-Free Subjects through 48 hours – Per-protocol Efficacy Analysis Set |

| | |
|--|--|
| | 14.2-5.3.S: Analysis of Opioid-Free Subjects through 72 hours – Primary Efficacy Analysis Set |
| | 14.2-5.3.1.S: Analysis of Opioid-Free Subjects through 72 hours – Per-protocol Efficacy Analysis Set |

Total lidocaine dose will be summarized (template 14.1-4.1) by treatment, site and surgeon within site. Lidocaine doses are found in dataset CM where CMCAT=SURGICAL MEDICATION / ANESTHESIA and CMDECOD=Xylocaine-epinephrine. Lidocaine was dosed 36 mg/carpule (or capsule) and will be converted from carpules/capsules to mg by multiplying the number of carpules used by 36.

Time from last lidocaine injection to first study treatment injection will be summarized (template 14.1-5.1) by treatment, site and surgeon within site.

Impacted third molars will be scored for each subject within jaw (maxillary and mandibular) and in total. Each full bony impaction is scored as 10 while partial impacted molars are scored as 1; erupted and soft tissue will be scored as 0. For example if a subject had 1 full bony impaction, 1 partial impaction, 1 erupted and 1 soft tissue, the subject's scores would be 10, 1, 0 and 0 respectively for a total impaction score of 11. Thus with each jaw the potential outcomes are 0, 1, 2, 10, 11 and 20 indicating, respectively, no impactions, a single partial bony impaction, two partial bony impactions, a single full bony impaction, one partial and one full bony impaction and two full bony impactions; and for the subject the potential outcomes are 0, 1, 2, 3, 4, 10, 11, 12, 13, 20, 21, 22, 30, 31 and 40. The impaction scores will be tabulated (template 14.1-5.1.1) by treatment, location (all, maxillary, mandibular), site and surgeon within site. Impaction scores will be presented from highest to lowest score.

Tooth impaction will be tabulated (template 14.1-6.2.1) by treatment, location, site and surgeon within site. Locations will be each tooth and maxillary (Tooth 1 and Tooth 16) and mandibular (Tooth 17 and Tooth 32). For maxillary and mandibular summaries if a subjects will be counted only once in each impaction category in the highest level of impaction reported where impaction levels from highest to lowest are 1-full bony, 2-partial bony, 3-soft tissue and 4-erupted.

Pharmacokinetic concentrations will be summarized (template 14.2-15.1.1) at each scheduled timepoint by treatment, site and surgeon within site. Plots of the mean PK concentration by time indicating each surgeon will be produced from this summary.

Pharmacokinetic parameters will be summarized (template 14.2-15.2.1) at each scheduled timepoint by treatment, site and surgeon within site.

Pacira Pharmaceuticals (Page X of Y) Protocol: 402-C-329
Table 14.1-4.1: Summary of Total Lidocaine Dose (mg) - by Site and Surgeon within Site - Safety Analysis
Set

| Site | Statistic | EXPAREL [N=XX] | Placebo [N=XX] |
|-----------------|--------------------|----------------|----------------|
| Overall | N | XX | XX |
| | Mean | XX.X | XX.X |
| | Standard Deviation | X.XX | X.XX |
| | Median | XX | XX |
| | Minimum | XX.X | XX.X |
| | Maximum | XX | XX |
| 100 | N | XX | XX |
| | Mean | XX.X | XX.X |
| | Standard Deviation | X.XX | X.XX |
| | Median | XX | XX |
| | Minimum | XX.X | XX.X |
| | Maximum | XX | XX |
| 100 - Surgeon 1 | N | XX | XX |
| | Mean | XX.X | XX.X |
| | Standard Deviation | X.XX | X.XX |
| | Median | XX | XX |
| | Minimum | XX.X | XX.X |
| | Maximum | XX | XX |
| 100 - Surgeon 2 | N | XX | XX |
| | Mean | XX.X | XX.X |
| | Standard Deviation | X.XX | X.XX |
| | Median | XX | XX |
| | Minimum | XX.X | XX.X |
| | Maximum | XX | XX |

Source: list SAS datasets used to create table
SAS X.Y

DDMONYYYYTHH:MM
program_name

Note to programmer: Sites to appear on this table are Overall, 100, 100-surgeon 1, 100-surgeon 2, 200, 300). Do not split a site across pages. Use this template also for tables:

Table 14.1-4.2: Summary of Total Lidocaine Dose (mg) - by Site and Surgeon within Site - Primary Efficacy Analysis Set

Table 14.1-4.3: Summary of Total Lidocaine Dose (mg) - by Site and Surgeon within Site - Secondary Efficacy Analysis Set

Table 14.1-4.4: Summary of Total Lidocaine Dose (mg) - by Site and Surgeon within Site - Per-protocol Efficacy Analysis Set

Table 14.1-5.1: Summary of Time from Last Lidocaine Dose to First Study Treatment Dose - by Site and Surgeon within Site - Safety Analysis Set

Table 14.1-5.2: Summary of Time from Last Lidocaine Dose to First Study Treatment Dose - by Site and Surgeon within Site - Primary Efficacy Analysis Set

Table 14.1-5.3: Summary of Time from Last Lidocaine Dose to First Study Treatment Dose - by Site and Surgeon within Site - Secondary Efficacy Analysis Set

Table 14.1-5.4: Summary of Time from Last Lidocaine Dose to First Study Treatment Dose - by Site and Surgeon within Site - Per-protocol Efficacy Analysis Set

Pacira Pharmaceuticals

(Page X of Y)

Protocol: 402-C-329

Table 14.1-6.1.1: Tabulation of Impaction Scores - by Site and Surgeon within Site - Safety Analysis Set

| Site | Location | Score [1] | EXPAREL [N=XX] | Placebo [N=XX] |
|---------|------------|-----------|----------------|----------------|
| | | | n (%) | n (%) |
| Overall | All | 40 | XX (XX.X) | XX (XX.X) |
| | | 31 | XX (XX.X) | XX (XX.X) |
| | | 30 | XX (XX.X) | XX (XX.X) |
| | | 22 | XX (XX.X) | XX (XX.X) |
| | | 21 | XX (XX.X) | XX (XX.X) |
| | | 20 | XX (XX.X) | XX (XX.X) |
| | | 13 | XX (XX.X) | XX (XX.X) |
| | | 12 | XX (XX.X) | XX (XX.X) |
| | | 11 | XX (XX.X) | XX (XX.X) |
| | | 10 | XX (XX.X) | XX (XX.X) |
| | | 4 | XX (XX.X) | XX (XX.X) |
| | | 3 | XX (XX.X) | XX (XX.X) |
| | | 2 | XX (XX.X) | XX (XX.X) |
| | | 1 | XX (XX.X) | XX (XX.X) |
| | | 0 | XX (XX.X) | XX (XX.X) |
| | Maxillary | 20 | XX (XX.X) | XX (XX.X) |
| | | 11 | XX (XX.X) | XX (XX.X) |
| | | 10 | XX (XX.X) | XX (XX.X) |
| | | 2 | XX (XX.X) | XX (XX.X) |
| | | 1 | XX (XX.X) | XX (XX.X) |
| | | 0 | XX (XX.X) | XX (XX.X) |
| | Mandibular | 20 | XX (XX.X) | XX (XX.X) |
| | | 11 | XX (XX.X) | XX (XX.X) |
| | | 10 | XX (XX.X) | XX (XX.X) |
| | | 2 | XX (XX.X) | XX (XX.X) |
| | | 1 | XX (XX.X) | XX (XX.X) |
| | | 0 | XX (XX.X) | XX (XX.X) |

[1] Sum of the impaction score for each tooth where full bony impaction = 10; partially bony = 1; other = 0
Score presented from highest to lowest level of impactions.

Source: list SAS datasets used to create table
SAS X.Y

DDMONYYYYTHH:MM
program_name

Note to programmer: Put each site and surgeon within site (Overall, 100, 100-surgeon 1, 100-surgeon 2, 200, 300) on a separate page. Use this template also for tables:

Table 14.1-6.1.2: Tabulation of Impaction Scores - by Site and Surgeon within Site - Primary Efficacy Analysis Set

Table 14.1-6.1.3: Tabulation of Impaction Scores - by Site and Surgeon within Site - Secondary Efficacy Analysis Set

Table 14.1-6.1.4: Tabulation of Impaction Scores - by Site and Surgeon within Site - Per-protocol Efficacy Analysis Set

Pacira Pharmaceuticals (Page X of Y) Protocol: 402-C-329
Table 14.1-6.2.1: Tabulation of Third Molar Impactions - by Site and Surgeon within Site - Safety Analysis Set

| Site | Location | Impaction | EXPAREL [N=XX] | Placebo [N=XX] |
|---------|-----------------|--------------|----------------|----------------|
| | | | n (%) | n (%) |
| Overall | Maxillary [1] | Full bony | XX (XX.X) | XX (XX.X) |
| | | Partial bony | XX (XX.X) | XX (XX.X) |
| | | Soft Tissue | XX (XX.X) | XX (XX.X) |
| | | Erupted | XX (XX.X) | XX (XX.X) |
| | Mandibular [1] | Full bony | XX (XX.X) | XX (XX.X) |
| | | Partial bony | XX (XX.X) | XX (XX.X) |
| | | Soft Tissue | XX (XX.X) | XX (XX.X) |
| | | Erupted | XX (XX.X) | XX (XX.X) |
| | Right Maxillary | Full bony | XX (XX.X) | XX (XX.X) |
| | | Partial bony | XX (XX.X) | XX (XX.X) |
| | | Soft Tissue | XX (XX.X) | XX (XX.X) |
| | | Erupted | XX (XX.X) | XX (XX.X) |
| | Left Maxillary | Full bony | XX (XX.X) | XX (XX.X) |
| | | Partial bony | XX (XX.X) | XX (XX.X) |
| | | Soft Tissue | XX (XX.X) | XX (XX.X) |
| | | Erupted | XX (XX.X) | XX (XX.X) |
| | Left Mandible | Full bony | XX (XX.X) | XX (XX.X) |
| | | Partial bony | XX (XX.X) | XX (XX.X) |
| | | Soft Tissue | XX (XX.X) | XX (XX.X) |
| | | Erupted | XX (XX.X) | XX (XX.X) |
| | Right Mandible | Full bony | XX (XX.X) | XX (XX.X) |
| | | Partial bony | XX (XX.X) | XX (XX.X) |
| | | Soft Tissue | XX (XX.X) | XX (XX.X) |
| | | Erupted | XX (XX.X) | XX (XX.X) |

[1] Subject counted only once at the highest level of impaction, presented from highest to lowest.

Source: list SAS datasets used to create table
SAS X.Y

DDMONYYYYTHH:MM
program_name

Note to programmer: Put each site (Overall, 100, 100-Surgeon 1, 100-Surgeon 2, 200, 300) on a separate page. Use this template also for tables:

Table 14.1-6.2.2: Tabulation of Third Molar Impactions - by Site and Surgeon within Site - Primary Efficacy Analysis Set

Table 14.1-6.2.3: Tabulation of Third Molar Impactions - by Site and Surgeon within Site - Secondary Efficacy Analysis Set

Table 14.1-6.2.4: Tabulation of Third Molar Impactions - by Site and Surgeon within Site - Per-protocol Efficacy Analysis Set

Pacira Pharmaceuticals (Page X of Y) Protocol: 402-C-329
Table 14.2-15.1.1: Summary of Pharmacokinetic Concentrations (ng/mL) - by Scheduled Collection Time, Site and Surgeon within Site - Pharmacokinetic Analysis Set
Site: Overall

| Time Point | Statistic | EXPAREL [N=XX] |
|------------------|--------------------|----------------|
| Prior to Surgery | n | xx |
| | Mean | xxx.x |
| | Standard Deviation | xxx.xx |
| | Median | xxx.x |
| | Minimum | xx |
| | Maximum | xxx |
| | n (%) BLQ | xx (xx.x) |
| 15 min | n | xx |
| | Mean | xxx.x |
| | Standard Deviation | xxx.xx |
| | Median | xxx.x |
| | Minimum | xx |
| | Maximum | xxx |
| | n (%) BLQ | xx (xx.x) |

BLQ = below limit of quantitation

Source: list SAS datasets used to create table
SAS X.Y

DDMONYYYYTHH:MM
program_name

Note to programmer: Do not split time point across pages. Time points to appear on this tables are Prior to Surgery, 15 min, 30 min and 1 hour, 2 hour, 4 hour, 8 hour, 12 hour, 18 hour, 24 hour, 30 hour, 36 hour, 42 hour, 48 hour, 54 hour, 60 hour, 66 hour, 72 hour, 84 hour, 96 hour, Day 7 and Day 10. Sites are Overall, 100, 100-Surgeon 1, 100-Surgeon 2, 200 and 300. Use this template for the following table:

Table 14.2-15.1.2: Summary of Pharmacokinetic Concentrations (ng/mL) - by Scheduled Collection Time, Site and Surgeon within Site - Subjects in Pharmacokinetic and Per-protocol Efficacy Analysis Sets

Pacira Pharmaceuticals

(Page X of Y)

Protocol: 402-C-329

Table 14.2-15.2.1: Summary of Pharmacokinetic Parameters - by Site and Surgeon within Site -
Pharmacokinetic Analysis Set

Site: Overall

| Parameter | Statistic | EXPAREL [N=XX] |
|-----------|--------------------|----------------|
| Cmax | n | xx |
| | Mean | xxx.x |
| | Standard Deviation | xxx.xx |
| | Median | xxx.x |
| | Minimum | xx |
| | Maximum | xxx |
| Tmax | n | xx |
| | Mean | xxx.x |
| | Standard Deviation | xxx.xx |
| | Median | xxx.x |
| | Minimum | xx |
| | Maximum | xxx |

BLQ = below limit of quantitation

Source: list SAS datasets used to create table
SAS X.Y

DDMONYYYYTHH:MM
program_name

Note to programmer: Do not split a parameter across pages. Parameters to appear on this table, in order of appearance, are Cmax, Early(0-2hr) Cmax, Early Tmax, Late (> 2hr) Cmax, Late Tmax, AUC(0-t), AUC(0-inf), Lambda_z, Half-life. Sites are Overall, 100, 100-Surgeon 1, 100-Surgeon 2, 200 and 300. Use this template for the following table:

Table 14.2-15.2.2: Summary of Pharmacokinetic Concentrations (ng/mL) - by Scheduled Collection Time, Site and Surgeon within Site - Subjects in Pharmacokinetic and Per-protocol Efficacy Analysis Sets

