[2] Tipping point is the value added to EXPAREL to reverse the statistical significance observed in the primary analysis.

Source: list SAS datasets used to create table
 SAS X.Y

DDMONYYYYTHH:MM
 program_name

Note to programmer: The raw SAS outputs from the procedures used to produce ALL 14.2-1.1 & 14.2-1.2 series tables should be saved as a possible appendix to the clinical study report (CSR). Use template 14.2-1.1.1 for the following tables:

Table 14.2-1.1.5: Sensitivity Analysis of AUC of NRS Pain Intensity Scores through 48 hours - Primary Efficacy Analysis Set - wWOCF with LOCF Single Imputation (Historical Imputation)

Pacira Pharmaceuticals (Page X of Y) Protocol: 402-C-329
Table 14.2-1.2: Summary of AUC of NRS Pain Intensity Scores through 48 hours - Primary Efficacy Analysis
Set - Analysis of Variance (ANOVA) Model Results - Multiple Imputation Results

| Effect | Model 1 | Model 2 |
|-------------------------------|--------------|--------------------------------|
| | Main Effects | Main Effects w/ Interaction |
| Treatment | 0.xxxx | 0.xxxx |
| Site | 0.xxxx | 0.xxxx |
| Treatment-by-Site Interaction | NA | 0.xxxx |

Note: AUC = area under the curve calculated using the trapezoidal method;
NRS = numeric rating scale at rest, where 0 = no pain and 10 = worst possible pain;
wWOCF + LOCF = imputation using the worst observation prior to use of rescue medication within a medication window and last-observation-carried-forward for missing values.
Model 1: ANOVA with main effects of treatment and site.
Model 2: ANOVA with main effects of treatment and site and treatment-by-site interaction.

Source: list SAS datasets used to create table
SAS X.Y

DDMONYYYYTHH:MM
program_name

Note to programmer: The raw SAS outputs from the procedures used to produce ALL 14.2-1.1 & 14.2-1.2 series tables should be saved as a possible appendix to the clinical study report (CSR).

| Pacira Pharmaceuticals | | (Page X of Y) | Protocol: 402-C-329 |
|--|--------------------|----------------|---------------------|
| Table 14.2-1.3: Summary of AUC of NRS Pain Intensity Scores through 48 hours by Site - Primary Efficacy Analysis Set - Multiple Imputation Results | | | |
| Site | Statistic | EXPAREL [N=XX] | Placebo [N=XX] |
| XXXX | N | xx | xx |
| | Mean | xxx.x | xxx.x |
| | Standard Deviation | xxx.xx | xxx.xx |
| | Median | xxx.x | xxx.x |
| | Minimum | xx | xx |
| | Maximum | xxx | xxx |
| Etc. | N | xx | xx |
| | Mean | xxx.x | xxx.x |

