12. MULTIPLE IMPUTATION EXAMPLE PROGRAM CODE

** Note: INPUT_DATA is the dataset that contains the NRS data with the wWOOF imputation performed for the rescue pain scores **;

** Step 1 use Markov-Chain Monte-Carlo (MCMC) method to create a monotonic missing pattern **;

** Note the value for the random seed should be fixed so that the results are reproducible **;

PROC MI DATA=INPUT_DATA SEED=M NIMPUTE=1000 OUT=OUTPUT_STEP1;

 BY TREATMENT;

 MCMC IMPUTE=MONOTONE NBITER=2000 NITER=1000;

 VAR TIME_POINT_LIST;

RUN;

** Step 2 – use regression on output dataset from Step 1 to impute missing values **;

** T_i is the variable containing the pain score from time i **;

PROC MI DATA=OUTPUT_STEP1 OUT=OUTPUT_STEP2;

 BY _IMPUTATION_;

 CLASS TREATMENT;

 MONOTONE REG(T_1 = TREATMENT / DETAILS);

 MONOTONE REG(T_2 = TREATMENT T_1 / DETAILS);

...

 MONOTONE REG($T_{(n-1)}$ = TREATMENT $T_1 T_2 T_3 \dots T_{(n-2)}$ / DETAILS);

 MONOTONE REG(T_n = TREATMENT $T_1 T_2 T_3 \dots T_{(n-1)}$ / DETAILS);

 VAR TREATMENT $T_1 T_2 T_3 \dots T_n$

RUN;

** Dataset OUTPUT_STEP2 is as an ADaM dataset, include in DEFINE.XML and transfers **;

** Step 3 derive endpoint using appropriate techniques by variable _imputation_ **;

** Endpoints are: AUC(0.25-48), AUC(0.25-24), AUC(0.25-72), SPI(0.25-24), SPI(0.25-48), **;

** SPI(0.25-72) and integrated rank assessment at 24, 48 and 72 hours **;

** Step 4 get summary statistics **;

** Summary step 4a get the mean of all imputation endpoint values for each subject **;

PROC SUMMARY DATA=OUTPUT_STEP2;

 BY TREATMENT USUBJID;

 VAR ENDPOINT_VARIABLE;

 OUTPUT OUT=SUMMARYSTATSA MEAN=ENDPOINTMEAN;

RUN;

** Dataset SUMMARYSTATSA is as an ADaM dataset, include in DEFINE.XML and transfers **;

** SUMMARYSTATSA also source for a data listing **;

** Summary step 4b use subject imputation means to derive summary statistics **;

PROC SUMMARY DATA=SUMMARYSTATSA;

 BY TREATMENT;

[figure not shown]
 VAR ENDPOINTMEAN;

 OUTPUT OUT=SUMMARYSTATSB N=N MEAN=MEAN STDDEV=STDDEV MEDIAN=MEDIAN
 MIN=MIN MAX=MAX;

RUN;

```
*** Step 5 analyze imputations **;  
ODS OUTPUT ESTIMATES=MIXEDSTATSA;  
PROC MIXED DATA= OUTPUT_STEP2 METHOD=TYPE3;  
    BY _IMPUTATION_;  
    CLASS TREATMENT SITE;  
    MODEL ENDPOINT_VARIABLE = TREATMENT SITE;  
    ESTIMATE 'EXPAREL - PLACEBO' TREATMENT 1 -1;  
RUN;  
  
ODS OUTPUT PARAMETERESTIMATES=MIXEDSTATSB;  
PROC MIANALYZE DATA= MIXEDSTATSA ALPHA=0.05 THETA0=0;  
    MODELEFFECTS ESTIMATE;  
    STDERR STDERR;  

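### Replacing site with surgeon in the addendum's ANOVA gives a 3-df surgeon p-value that mixes two between-site contrasts with one surgeon contrast

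*SAP*

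**What the plan says.** The SAP's efficacy ANOVA has treatment and site as main effects (SAP 7.6.2.1; the example code in SAP 12 has "MODEL ENDPOINT_VARIABLE = TREATMENT SITE"). Template Table 14.2-1.2 prints p-values for the effects in that model and in a second one: "Model 2: ANOVA with main effects of treatment and site and treatment-by-site interaction".

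Addendum Section 3 then says that "The effect of surgeon will be determined by replacing the site effect in the efficacy analysis of variance with surgeon". The same sentence adds a second, descriptive part: summaries split by surgeon inside each site where suitable, with a pointer to the addendum's Section 2. Table B repeats the instruction for the AUC tables: "Replace site effect in ANOVA with surgeon". For the opioid-free tables it makes surgeon the stratification factor instead of site.

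On what counts as a surgeon, Table B says "For site 100 create new pages in the table for each surgeon at site 100". The programmer note for the lidocaine table reads "Sites to appear on this table are Overall, 100, 100-surgeon 1, 100-surgeon 2, 200, 300", and the pharmacokinetic shells agree: "Sites are Overall, 100, 100-Surgeon 1, 100-Surgeon 2, 200 and 300". No visible shell splits site 200 or site 300.

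**The concern.** The question asked is whether surgeon matters. Once site leaves the model and the surgeon factor has levels 100-1, 100-2, 200 and 300, the null hypothesis of the surgeon row is that all four means are equal. That null fails if any site differs from another, even when the two surgeons at site 100 are identical. The interaction row implied by the reused template has the same structure.

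At stake is the meaning of two p-values in six tables: 14.2-1.2.1.S, 14.2-1.2.1.S.1, 14.2-2.2.S, 14.2-2.2.1.S, 14.2-3.2.S and 14.2-3.2.1.2. A study report could carry a site difference under a surgeon label. Table B lists no AUC output that compares the two site-100 surgeons directly.

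**Working it through.** **Inputs from the documents.** Two-sided 0.05 (SAP 7.6.2.1). SD of AUC 100 to 128, and a design difference of 66 at SD 100, or 0.66 SD (Protocol 15.3, SAP 8). At least 100 EXPAREL and 50 placebo subjects, about 175 in total (SAP 4). 2:1 allocation under Amendment 2, with at least 50 treated per arm under that amendment (Protocol 15.3).

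**Assumptions.** The documents give neither site shares nor site differences, nor the final size of the Amendment 2 set. I take N = 150 (50 placebo at 2:1), treatment split 2:1 in every group, site 100 divided equally between its two surgeons, and the rest divided equally between sites 200 and 300. A smaller set would lower the rejection rates below.

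**The plan's own figure.** For 50 per group the noncentrality is 0.66 × √(50/2) = 3.30, which gives 90.4% power; 86/130 gives 90.6%. The stated 90% is reproduced. The documents state no figure for the surgeon test.

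**Degrees of freedom.** The four group means give three independent contrasts: (i) 100-1 minus 100-2; (ii) the site 100 average minus site 200; (iii) the site 100 average minus site 300. Only (i) compares surgeons within a site. Treatment-by-group splits in the same 1 + 2 way.

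**Planned test with identical site-100 surgeons.** Suppose one other site, holding a share p of subjects, is shifted by d SD. The planned F test has 3 and 150 − 5 = 145 df, critical value 2.667, and noncentrality λ = N·p·(1 − p)·d². With d = 0.5:

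| Share at site 100 | p | λ | Planned 3-df test rejects | Nested 1-df test rejects |
|---|---|---|---|---|
| 60% | 0.20 | 150 × 0.20 × 0.80 × 0.25 = 6.00 | 51% | 5% |
| 50% | 0.25 | 150 × 0.25 × 0.75 × 0.25 = 7.03 | 58% | 5% |
| 40% | 0.30 | 150 × 0.30 × 0.70 × 0.25 = 7.88 | 63% | 5% |

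The nested test compares treatment + site + surgeon(site) with treatment + site, so a site shift adds nothing to its noncentrality. A simulation of 20,000 trials with half the subjects at site 100 gave 58.6% for the planned test and 5.0% for the nested one. With no shift the rates were 5.2% and 5.1%.

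**Wider assumptions, 50-unit shift.** The lowest rate comes from shares 80/10/10, N = 150 and SD 128: λ = 150 × 0.10 × 0.90 × (50/128)² = 2.06, giving 19%. The highest comes from equal thirds, N = 174 and SD 100: λ = 174 × (1/3) × (2/3) × 0.25 = 9.67, giving 73%.

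**Interaction.** Suppose the treatment effect differs by d SD at one site only, with p = 0.25. Then λ = N × (2/9) × p(1 − p) × d², with 3 and 142 df. For d = 0.5, λ = 1.56 and the test rejects 15% of the time. For d = 0.66, λ = 2.72 and it rejects about 24% to 25%. The nested 1-df interaction test stays at 5%.

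**Sensitivity to a real surgeon difference.** Take half the subjects at site 100, surgeons 0.66 SD apart, and a site 100 average equal to the other sites. Then λ = 75 × 0.33² = 8.17, giving 65% power for the planned test and 81% for the nested test. This loss is not general. If one surgeon differs by 0.66 SD from all three other groups, λ = 150 × 0.25 × 0.75 × 0.66² = 12.25, and the planned test has 84%.

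**The case against.** - **The method has a second half.** The addendum also promises summaries by surgeon within site and points to its Section 2, which is not in the text available here and may define the coding or add within-site AUC summaries. This stands as a limit on the point. The replacement sentence and Table B's instruction still say that site leaves the model.
- **Most of the swapped tables serve the treatment comparison.** Of the 14 efficacy tables, 14.2-1.1.1.S and 14.2-1.1.6.S follow by title a template that reports only the treatment difference, and the six opioid-free tables follow a stratified layout with no surgeon p-value. A four-level factor still adjusts fully for site, so all eight are sound. This stands, and it confines the point to the other six.
- **A reader might infer that the test will declare a surgeon effect where none exists.** The documents do not support that. They do not say how many surgeons worked at sites 200 and 300. With one at each, surgeon and site are inseparable there, and a difference could belong to either. The tenable criticism is that the two cannot be told apart.
- **A reader might infer that the surgeon p-value will be used to explain the efficacy result.** No document says so. Section 3 covers additional summaries, Table B's tables explore the surgeon effect, and no decision rule is attached to them.
- **The interaction row is an inference.** The addendum never names a treatment-by-surgeon term; it follows from reusing template 14.2-1.2.
- **The site p-value is still printed elsewhere.** Table 14.2-1.2 lets a reader see when sites differ. That helps, but it gives no estimate of surgeon 1 against surgeon 2.

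**Conclusion.** The point holds for six exploratory tables. Their surgeon p-value, and the interaction p-value implied by the template, combine two between-site contrasts with one surgeon contrast, so they cannot answer the surgeon question alone. The degrees-of-freedom argument rests only on the four levels in the visible shells.

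The size is illustrative: about 51% to 63% rejection against 5% nested for a 0.5 SD shift at one site, N of about 150 and 40% to 60% of subjects at site 100. It widens to 19% to 73% for a 50-unit shift when shares run from equal thirds to 80/10/10, SD from 100 to 128 and N from about 150 to 175. Without site differences the planned test keeps its 5% level.

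Nothing here touches the primary or secondary efficacy conclusions. It is worth correcting because it changes what the surgeon tables can conclude.

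**What to change.** In addendum Section 3 and Table B, for the six tables:

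- Keep site and add surgeon nested within it: AUC = treatment + site + surgeon(site).
- Report as the surgeon effect the 1-df contrast of surgeon 1 against surgeon 2 at site 100, with its estimate and 95% CI.
- Report the matching 1-df difference in treatment effect between those two surgeons, with its 95% CI, from a model that keeps treatment-by-site.
- Label any four-level p-value as site and surgeon combined.
- Check that addendum Section 2 agrees.

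The cost is a sentence in the addendum and a model term or contrast in the program, with no new data. The surgeon contrast draws on site 100 only and will be imprecise, but in the layout shown the other sites carry no information on surgeon separate from site.
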